Sleep Extension and Behavior of Young Children

University of Massachusetts, Amherst Protocol Record 2015-2739

Protocol first approved: 11/9/15

Submitted to ClinicalTrials.gov: 2/20/18

Study Protocol

Sleep Measures

Actigraphy. Actiwatch Spectrum wristwatches (Spectrum 2; Philips Respironics) were used to measure sleep and wake onset times and confirm that experimental manipulations were followed. The Actiwatch has off-wrist detection and a triaxial accelerometer that samples activity at 32Hz, with a sensitivity of <0.01g. Activity was stored in 15-second epochs. Actigraphy is a reliable index of time spent asleep and awake in developmental populations.

Polysomnography (PSG). Polysomnography electrode caps (EasyCap) were used to record overnight sleep physiology. Data was collected from 24 EEG electrodes, 2 electrooculogram electrodes, and 2 electromyogram electrodes (affixed to the chin) referenced to a mid-forehead ground (FPz) and referenced to Cz and contralateral mastoids.

Sleep Diary. Sleep diaries were used to validate scoring of actigraphy data. Caregivers logged their child's sleep latency, sleep onset time, and morning wake onset time each day of the experimental protocol.

Behavioral Measures

Go/No-Go Task. A developmentally appropriate Go/No-Go task was used to assess inhibitory control. In Go trials (75% of trials), images of various animals (e.g., giraffe, elephant, panda) were presented. In No-Go trials (25% of trials), a chimpanzee was presented. Displayed images were 3 inches in height and 4 inches in length, centered on a 14-inch computer screen positioned approximately 15 inches from participants.

Each trial began with the presentation of an animal image for 500 ms. Children were instructed to respond, via a button press on a computer mouse, for all of the animals (Go trials) except for the chimpanzee for which they were to inhibit their response (No-Go trials). A blank screen was presented for 500 ms between trials. Children were given 12 practice trials to ensure they understood task instructions. Subsequently, test trials were presented in 2 blocks of 60 trials each. Two pseudo-random trial orders were used for all participants (for evening and morning sessions). Trial order was counterbalanced across sessions (morning and evening), conditions (baseline and extension), and participants.

Procedure

Procedures were approved by the local Institutional Review Board. Accordingly, researchers described the procedures and caregiver consent was obtained at an in-home visit. During this initial visit, the sleep diary was given to the caregiver. Child assent was obtained and the Actiwatch was fitted to child's non-dominant wrist. Children and caregivers were shown how to use the Actiwatch and an instruction sheet was provided for future reference. Caregivers were asked to oversee the child's use of the Actiwatch and complete the sleep diary each day. Children and caregivers were instructed that the child must maintain their habitual wake time across the two 5-day testing periods. For consistency, maintaining habitual wake time was intended to ensure that sleep extension was a product of earlier sleep onset time and not delayed wake time. Children's wake time is also often constrained by bus schedules and school start times.

There were two conditions, a baseline condition and a sleep extension condition. During the baseline condition, children followed their normal bedtime routine for five consecutive nights. During the extension condition, caregivers were instructed to put their child to bed 90 minutes earlier than their habitual bedtime for five consecutive nights. Caregivers were provided a list of

tips to aid in implementing the earlier bedtime.

On the last night of the baseline and extension conditions, children, accompanied by a caregiver, arrived at the sleep laboratory approximately one hour before their habitual (baseline condition) or extended (extension condition) bedtime. After settling in, children completed a baseline assessment of the Go/No-Go task. Children were then fitted with a PSG cap. Children and caregivers slept in the lab (in separate beds in the same room) overnight. The following morning, children woke at their habitual wake time. The PSG cap was removed and children were given time to complete their normal morning routine. Children then completed the morning assessment of the Go/No-Go task. This concluded the overnight visit. At the end of each in-lab visit, the Actiwatch and sleep diaries were collected. Caregivers were provided monetary compensation and children chose an age-appropriate prize.

There was approximately one week between the baseline and extension conditions. The order of conditions was counterbalanced across participants. Whenever possible, the conditions were matched for the day of the week they took place.

Statistical Analyses

Statistical analyses were performed in SPSS, and an alpha of 0.05 was used to determine significance.

Sleep

Actigraphy data was used to assess the efficacy of the sleep extension intervention in extending sleep time from baseline. Children and their caregivers were instructed to press an event marker on the Actiwatch when the child went to sleep and woke up each day. Event markers and sleep diary entries were used to confirm the start and end time of each sleep bout. Actiware software (Philips Respironics) was then used to differentiate intervals of sleep and wake. Sleep onset time was set at the first of three consecutive minutes of sleep and wake onset time was set at the last of five consecutive minutes of sleep. Total sleep time was defined as the total minutes scored as sleep between sleep onset and wake onset.

A repeated-measures ANOVA was used to compare sleep-timing variables (i.e., sleep onset and total sleep time) between the baseline and extension conditions across groups. In these models, sleep-timing variables were independently entered as outcome variables. Condition (baseline and extension) was entered as a within-subjects factor and group (ADHD and TD) was entered as a between-subjects factor.

Polysomnography was scored according to the revised American Academy of Sleep Medicine manual by a trained researcher. Due to recording error, five participants in the TD group did not have usable PSG data.

Repeated-measures ANOVAs were used to compare PSG outcome variables (i.e., total sleep time and time spent in distinct sleep stages) between conditions and groups. Here too, condition was entered as a within-subjects factor and group as a between-subjects factor.

Inhibitory Control

To determine whether sleep extension improved inhibitory control in children with and without ADHD, a repeated-measures ANOVA was used. In this model, inhibitory control, as measured by accuracy (% correct) on No-Go trials, was entered as the outcome variable. Condition and time (evening and morning) were entered as within-subject factors and group was entered as a between-subjects factor. Separate repeated-measures ANOVAs were then run independently

for each group to assess group-specific changes in inhibitory control following the sleep manipulation.

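### Go/No-Go trial order is counterbalanced by design but left out of the No-Go ANOVAs, so any difficulty difference between the two orders would cost precision in whichever effect the layout aliases with order

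*Combined protocol and SAP*

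**What the plan says.** Study Protocol, Behavioral Measures, Go/No-Go Task: "Two pseudo-random trial orders were used for all participants (for evening and morning sessions". It continues: "Trial order was counterbalanced across sessions (morning and evening), conditions (baseline and extension), and participants". No table shows which child received which order at which session.

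The same section gives the session length ("test trials were presented in 2 blocks of 60 trials each") and the share of inhibition trials ("In No-Go trials (25% of trials), a chimpanzee was presented").

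Statistical Analyses, Inhibitory Control: "inhibitory control, as measured by accuracy (% correct) on No-Go trials, was entered as the outcome variable". The model terms are then listed: "Condition and time (evening and morning) were entered as within-subject factors and group was entered as a between-subjects factor". For the two groups, "Separate repeated-measures ANOVAs were then run independently". Trial order appears in none of these models.

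The Procedure section describes a different balancing factor, the order of the two visits: "The order of conditions was counterbalanced across participants". How visit order and trial order were combined is not stated. A visit-order term would therefore absorb a trial-order difference only if the two were tied together, and in any case no such term is listed.

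**The concern.** Counterbalancing a nuisance factor stops it from shifting the average result. It does not take the factor's variation out of the error term; the factor has to be in the model for that.

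Each child has four sessions (two conditions by two times of day) and only two stimulus orders, A and B. Suppose a child receives A then B at one visit and B then A at the other. Order is then fully aliased, within that child, with Condition × Time. Children given the reverse layout cancel the average shift, but an ANOVA with only condition, time and group treats the opposite shifts as unexplained differences between children. Condition × Time asks whether the change across the laboratory night differs between the baseline and extended schedules. Group × Condition × Time asks whether that difference is the same in ADHD and TD. Both use the same error term. What is at stake is power for these two tests, and for Condition × Time within each group.

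**Working it through.** The plan states no sample size, SD, effect size or order difference for this outcome, so there is no figure of its own to reproduce.

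**Inputs from the documents.** Two orders; four sessions per child; 2 × 60 = 120 test trials per session, of which 25%, or 30, are No-Go.

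**Assumptions (not in the documents).**
- d, the mean A-minus-B difference in No-Go accuracy: 2 to 5 points, which is 0.6 to 1.5 of the 30 No-Go trials.
- s, the SD of independent session error: 8.4 to 15 points. The lower value is binomial sampling error alone at an assumed 70% correct: 100 × √(0.7 × 0.3 / 30) = 8.37. It changes with accuracy (9.1 at 50%, 6.5 at 85%), and real session-to-session variation adds to it.
- Where power or type I error is quoted: 40 children, evenly split over the sequences.

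**Contrast algebra.** Code each session +d/2 under order A and −d/2 under order B. Write L = (extension morning − extension evening) − (baseline morning − baseline evening). Without an order effect, L has variance 4s². The Time and Condition contrasts, each averaged over the other factor, have variance s².

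For a child with A-B at baseline and B-A at extension, L shifts by (d/2 + d/2) − (−d/2 − d/2) = +2d. For the reverse layout it shifts by −2d. With equal numbers the mean shift is 0 and the added variance is 4d². The multiplier is (4s² + 4d²)/(4s²) = 1 + d²/s².

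Variance added by an omitted order effect, in units of d²:

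| Possible layout | Condition | Time | Condition × Time |
|---|---|---|---|
| 1. Orders swapped between conditions, two sequences | 0 | 0 | 4 |
| 2. Four balanced sequences | 0 | 0.5 | 2 |
| 3. Same evening/morning assignment in both conditions | 0 | 1 | 0 |
| 4. One order per condition | 1 | 0 | 0 |

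The mean shift is 0 in every cell when assignment is balanced. Layouts 1 and 2 fit the counterbalancing sentence best. Layout 4 fits poorly with orders described as being for the evening and morning sessions.

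**Condition × Time error-variance multiplier, layout 1 (1 + d²/s²):**

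| | s = 8.4 | s = 10 | s = 15 |
|---|---|---|---|
| d = 2 | 1.06 | 1.04 | 1.02 |
| d = 3 | 1.13 | 1.09 | 1.04 |
| d = 5 | 1.35 | 1.25 | 1.11 |

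Layout 2 gives half of each increase; for example, 1 + 0.354/2 = 1.18 at d = 5, s = 8.4.

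**Power.** With s = 10 and an effect on L of 9.1 points, set to give 80% power when d = 0, omitting order gives 78% (d = 2) or 71% (d = 5) under layout 1, and 79% or 75% under layout 2. With order in the model, power is about 80% throughout. At s = 8.4 under layout 1, simulated power without the term is 79% (d = 2) and 69% (d = 5).

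**Type I error.** In 20,000 simulated trials with d = 5 and s = 10, the Condition × Time test rejected at 0.029, 0.038, 0.047 and 0.051 under layouts 1 to 4. The nominal level is 0.05, so where order matters the test is conservative.

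**Imbalance within a group.** Under layout 1, if a share p of a group has one sequence, the group's mean L shifts by (2p − 1) × 2d. A purely illustrative 12:8 split of 20 children gives 0.2 × 2d = 0.4d, or 1.2 points at d = 3 and 2.0 points at d = 5. At 10:10 it is 0.

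**The case against.** The strongest reply is that nothing shows the orders to differ. Both use the same task, the same No-Go animal, the same timing and the same share of No-Go trials, and a d of 5 points means 1.5 trials out of 30 lost to sequence alone. At d = 2 the loss is negligible, and a larger s shrinks every figure. This stands: the size is conditional throughout, and no difference between the orders should be called known.

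The Condition main effect also bears most directly on the stated question, whether extension improved inhibitory control. The evening test takes place on the last of five nights, so it already follows four extended nights, and Condition × Time isolates only the final one. Condition is untouched under layouts 1 to 3. This too stands.

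Four stronger readings are tempting and are not supported:

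- A reader might infer that any difficulty difference must inflate Condition × Time. Under layouts 3 and 4 it does not, and the sequence table is not given.
- A reader might infer bias or excess false positives. With balanced assignment the mean shift is zero and the test rejects too rarely.
- A reader might infer that the per-group ANOVAs are biased because balance is described only across participants. That needs imbalance within a group, and the documents report neither sequence counts nor group sizes.
- A reader might extend the point to morning-only or evening-only comparisons of the two conditions. The plan names none.

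What the objection does not answer is that a factor the trial deliberately balanced is missing from every No-Go model, and that under each layout examined some tested effect would absorb d.

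**Conclusion.** The point holds as a minor one about precision. Under the swapped layout, an omitted order difference multiplies the Condition × Time error variance by about 1.02 to 1.35 for the assumed ranges of d and s, or by about 1.01 to 1.18 with four sequences. If each child kept one evening/morning assignment, the cost falls on Time instead. These figures rest on assumed values of d and s and on an inferred layout; if d is 0 there is no loss. The omission does not threaten a conclusion drawn from the Condition main effect unless one order was used per condition, and even then balanced assignment leaves lost precision and no bias.

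**What to change.** In the joint and per-group No-Go analyses, use a mixed model with the trial order at each session (A or B) as a two-level fixed term beside condition, time and group. This works under any layout. In a per-group model under the swapped layout, both sequences must occur in that group for order to be separable from Condition × Time.

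If the SPSS repeated-measures ANOVA is kept, enter the actual counterbalancing sequence as a between-subjects factor with as many levels as there were sequences. A two-level factor is enough only if there were two.

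State the sequence table, report the A-minus-B difference in No-Go accuracy, and tabulate the sequences within ADHD and TD.

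The cost is one degree of freedom in the mixed model. In the joint ANOVA, two sequences crossed with group make 4 cells in place of 2, which costs two error degrees of freedom; four sequences crossed with group make 8 cells, which costs six. No new data or children are needed, but the record of which order was used at each session must be available. If the analyses have already been run, the same model can be reported as a sensitivity analysis.

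### Condition order is counterbalanced, but no ANOVA has an order or period term, so a mean visit-1-to-visit-2 change inflates the error of the Condition tests

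*Combined protocol and SAP*

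**What the plan says.** The Procedure section has every child do a baseline and an extension condition, each ending in one overnight lab visit with Go/No-Go testing in the evening and the next morning. On spacing it says: "There was approximately one week between the baseline and extension conditions". On sequence it says: "The order of conditions was counterbalanced across participants". Whether the balance also held within ADHD and within TD is not stated. The Go/No-Go Task paragraph adds a second counterbalancing, of the stimulus lists: "Trial order was counterbalanced across sessions (morning and evening), conditions (baseline and extension), and participants".

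Statistical Analyses names the factors of each model. For No-Go accuracy: "Condition and time (evening and morning) were entered as within-subject factors and group was entered as a between-subjects factor". For PSG: "Here too, condition was entered as a within-subjects factor and group as a between-subjects factor". The actigraphy ANOVA has the same two factors. After the joint No-Go model, "Separate repeated-measures ANOVAs were then run independently" for each group. No model includes order, sequence, period or visit. The No-Go factor called time is evening versus morning within a visit, so it does not stand in for period. The PSG paragraph also reports that "five participants in the TD group did not have usable PSG data".

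**The concern.** Counterbalancing protects the estimate, but it does not by itself protect the precision of the test. If children do better on No-Go at the second visit because they know the task, or sleep differently on their first lab night, that shift adds to the extension-minus-baseline difference in children who had extension second and subtracts from it in the others. A model without order treats this known pattern as random scatter between children.

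The 12 practice trials and the balanced stimulus lists reduce learning from one visit to the next but do not remove it. The documents do not show that a visit effect occurred; the design makes one plausible.

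Two things are at stake. The Condition and Condition × Group tests lose power, so a null result in one diagnostic group could partly reflect avoidable error variance. And if order is uneven within a group, part of the visit effect is read as an effect of sleep extension. The Group main effect is not biased, because every child contributes both visits. Actigraphy is less exposed, because only the last of its five nights per condition is spent in the lab.

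**Working it through.** **Inputs.** From the documents: two conditions, two periods, order counterbalanced across participants, the model factors above, alpha 0.05, and five TD children without usable PSG. The documents give no sample size, SD, effect size or power, so there is no stated figure to reproduce. Assumed for illustration: 20 children per group, SD of within-child differences 15 points, and a mean second-minus-first-visit change p of 2.5, 5 or 10 points.

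**1. Model.** For each child, extension minus baseline is d = τ + s·p + e, with s = +1 if extension came second, s = −1 if it came first, and e of variance SD².

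**2. Balanced order, order omitted.** The mean of s is 0, so p drops out of the estimate of τ. The variance of d becomes SD² + p², a factor of 1 + (p/SD)²: 1 + 6.25/225 = 1.028, 1 + 25/225 = 1.111 and 1 + 100/225 = 1.444. The expected error mean square is slightly larger, because p² is multiplied by n/(n−1) = 20/19 in one group, or N/(N−2) = 40/38 in both. The factors are then 1.029, 1.117 and 1.468.

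**3. Effect on the tests** (simulation, 10/10 order split in each group; without order / with order):

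| p | One-group Condition, type I error | One-group Condition, power at τ = 7 | Condition × Group, power at difference 10 |
|---|---|---|---|
| 0 | – | 51.0% / 50.8% | 53.6% / 53.5% |
| 2.5 | 4.7% / 5.0% | 49.9% / 50.8% | 52.8% / 53.8% |
| 5 | 3.9% / 5.0% | 46.3% / 50.5% | 49.4% / 53.8% |
| 10 | 1.9% / 4.9% | 34.6% / 50.7% | 37.4% / 53.6% |

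**4. Check in standardised units.** A separate calculation for the joint Condition test took 40 children in all, τ/SD = 0.5 and balanced order. With p/SD = 0.25, 0.5, 0.75 and 1.0, power without order is 85.5%, 80.8%, 72.6% and 60.5%, against 86.8% with order and order × group in the model. Type I error without order is 4.4%, 2.8%, 1.4% and 0.5%. Only p/SD matters, so these figures apply equally to PSG outcomes in minutes.

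**5. Uneven order.** If a share f of a group had extension second, that group's Condition estimate shifts by (2f − 1)p, and Condition × Group shifts by 2(f_ADHD − f_TD)p. For 12/8 in one group and 8/12 in the other, the interaction shift is 2 × (0.6 − 0.4)p = 0.4p, or 1, 2 and 4 points. Simulated type I error without order is 5.1%, 5.7% and 6.4%. With order in the model the bias is 0 and type I error is 4.9% to 5.2%.

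**6. PSG subset.** Suppose 20 TD children split 10/10 and five are lost at random. There are C(20,5) = 15,504 ways to lose five.
- 8/7 remaining: 2·C(10,3)·C(10,2)/15,504 = 10,800/15,504 = 70%; TD shift p/15.
- 9/6 remaining: 2·C(10,4)·C(10,1)/15,504 = 4,200/15,504 = 27%; TD shift p/5.
- 10/5 remaining: 2·C(10,5)/15,504 = 504/15,504 = 3%; TD shift p/3.

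If ADHD stays balanced at 10/10, Condition × Group shifts by the full TD amount and the Condition effect averaged over groups by half of it. Even at 10/5 with p/SD = 0.5, simulated type I error without order is about 5%, because the inflated error offsets the bias.

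**The case against.** The strongest reply is that the design already deals with validity. With balanced order the Condition estimate is unbiased and the test errs on the safe side, so the omission cannot produce excess false positives. The size is also unknown. Over the lower part of the assumed range the loss is only about 1 to 4 power points, and nothing in the documents points to a shift as large as two-thirds of the SD. The bias route needs an imbalance that the documents do not report: silence about balance within groups is not evidence against it, and the likeliest PSG split after losing five children is a mild 8/7.

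All of this is fair, and it limits the point to efficiency plus a check on order balance. It does not remove it: a test known to be conservative is a cost in a study asking whether each group benefits, and the remedy is practically free.

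Three further qualifications stand.
- Only the mean shift can be removed. Child-to-child variation in change stays in the error even with order in the model.
- In the No-Go model, a shift common to evening and morning does not touch the Condition × Time test.
- The text is in the past tense and already reports lost recordings, so an order term added now would be post hoc and should be labelled so.

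**Conclusion.** The concern holds. Order is a design factor, every listed ANOVA omits it, and any mean visit-to-visit shift therefore inflates the error of the Condition and Condition × Group tests. With order balanced within groups the result is conservative tests without bias. Under the assumed 20 per group and SD of 15, the power loss is negligible at p = 2.5, about 4 percentage points at p = 5 and about 16 at p = 10. Bias arises for a group's Condition effect only if order is uneven within that group, and for Condition × Group only if the split differs between ADHD and TD. The actual size cannot be fixed from the documents, because sample size, SD, effect and visit change are all assumed. This is a change that should be made; it does not invalidate the analysis.

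**What to change.** Add order (baseline first or extension first) as a between-subjects factor to the No-Go and PSG ANOVAs, including the group-specific No-Go ANOVAs, and for consistency to the actigraphy ANOVAs. Condition × Order then carries the period effect, and the Condition effect should be averaged equally over the two orders. Report the order split by group and again in the PSG subset. If the stated ANOVAs have already been run, show both sets of results and say that order was added later. The order term does not separate carryover from other sequence differences, and this should be acknowledged.

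If a mixed model is preferred for No-Go, include period and a child-by-visit random effect as well as the child effect. With four observations per child, 20 children and residual SD 10 (all but the four observations assumed), a child effect alone gave type I error of 8.3% and 14.6% at visit-level SDs of 5 and 10; the ANOVA with order gave 5.0% in both.

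The cost is a rerun in SPSS with one factor that should already be known for each child. It uses one error degree of freedom in each group-specific model, and two in a full factorial with group (order and order × group).

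### The mixed ANOVAs pool ADHD and TD variances, so the 5% error rate of the group × condition and condition tests is not secured if group sizes and spreads both differ, as may be so for PSG.

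*Combined protocol and SAP*

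**What the plan says.** The plan is the Statistical Analyses section of the combined protocol and SAP. It names SPSS and says that "an alpha of 0.05 was used to determine significance". Three sets of analyses put both diagnostic groups in one model:

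- Sleep, actigraphy (sleep onset and total sleep time): "Condition (baseline and extension) was entered as a within-subjects factor and group (ADHD and TD) was entered as a between-subjects factor".
- Sleep, polysomnography (total sleep time and time in each stage): "Here too, condition was entered as a within-subjects factor and group as a between-subjects factor".
- Inhibitory Control (No-Go accuracy): "Condition and time (evening and morning) were entered as within-subject factors and group was entered as a between-subjects factor".

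On PSG data the Sleep subsection adds: "Due to recording error, five participants in the TD group did not have usable PSG data". It mentions no such loss in the ADHD group.

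For inhibitory control only, the plan also has within-group analyses: "Separate repeated-measures ANOVAs were then run independently" for each group.

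The documents give no group sizes or SDs. They describe no check of equal variances between groups, no separate-variance test, no heterogeneous-variance model and no robust standard error.

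**The concern.** Every within-child factor has two levels. Each within-child effect in these models is therefore a t-test on one contrast score per child, with the error variance pooled over ADHD and TD. Sphericity corrections are irrelevant with two levels. The assumption that matters is equal variance of the contrast in the two groups, and the plan does not address it.

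Pooling does little harm if the groups are the same size. If they are not, the larger group dominates the pooled variance. The test is then too liberal when the smaller group is the more variable one, and too conservative when the larger group is.

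Two features make this more than a textbook caution:

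- The groups are defined by diagnosis, not by randomisation, so the design gives no reason to expect equal spread.
- The one documented data loss falls on one group only.

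At stake is the formal test of whether extension works differently in ADHD and TD children and, under Type III means, the overall extension effect in the same models.

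**Working it through.** **Inputs from the documents.** Alpha 0.05; two conditions; two groups; five TD children without usable PSG; No-Go trials are 25% of 2 × 60, that is 30 per session.

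**Assumptions, because the documents are silent.** Equal recruitment of 15, 20, 25 or 30 per group, less five TD for PSG; an SD ratio of the contrast of up to 2 in either direction; normal contrasts; unweighted (Type III) means for the condition effect.

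**Step 1: the test.** Let d be a child's extension-minus-baseline difference, with mean m, SD s and size n in each group. The ANOVA uses

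s_p² = [(n1−1)s1² + (n2−1)s2²] / (n1+n2−2).

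- Group × condition: t = (m1−m2) / √[s_p²(1/n1+1/n2)].
- Condition, unweighted: t = ½(m1+m2) / {½√[s_p²(1/n1+1/n2)]}.

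The true variance of m1−m2, and of m1+m2, is s1²/n1 + s2²/n2. Both tests are therefore distorted to the same degree. If n1 = n2, the pooled and true variances agree on average, which is why equal groups are nearly safe.

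**Step 2: one case by hand.** ADHD 15, TD 10.

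- TD SD twice ADHD SD (1 v 2): s_p² = (14×1 + 9×4)/23 = 2.174. The variance used is 2.174 × (1/15+1/10) = 0.362; the true variance is 1/15 + 4/10 = 0.467. The standard error is √(0.362/0.467) = 0.88 of what it should be, so the test is liberal.
- ADHD SD twice TD SD (2 v 1): s_p² = (14×4 + 9×1)/23 = 2.826. The variance used is 0.471; the true variance is 4/15 + 1/10 = 0.367. The standard error is √(0.471/0.367) = 1.13 times too large, so the test is conservative.

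**Step 3: actual error of the nominal 5% test**, by numerical integration over the two sample variances. With equal SDs the method returns 0.0500 for 20 v 20 and for 15 v 20, which reproduces the plan's alpha.

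| ADHD v TD | ADHD SD 2× | ADHD SD 1.5× | Equal | TD SD 1.5× | TD SD 2× |
|---|---|---|---|---|---|
| 15 v 10 | 3.0% | 3.6% | 5.0% | 7.1% | 8.7% |
| 20 v 15 | 3.5% | 4.0% | 5.0% | 6.4% | 7.5% |
| 25 v 20 | 3.8% | 4.2% | 5.0% | 6.1% | 6.9% |
| 30 v 25 | 4.0% | 4.3% | 5.0% | 5.9% | 6.5% |
| 20 v 20 | 5.2% | 5.1% | 5.0% | 5.1% | 5.2% |
| 10 v 20 (assumed 2:1) | 11.4% | 8.6% | 5.0% | 2.7% | 1.9% |

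Simulation with 100,000 runs per setting agrees. For 10 v 20 with the smaller group's SD doubled, it gives 11.2% (interaction) and 11.3% (condition); with the larger group's SD doubled, 1.9% for both.

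**Step 4: the alternative.** A Welch test of the interaction, and its Satterthwaite counterpart for the condition effect, held 4.9% to 5.1% in every setting simulated.

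**Step 5: could the No-Go spreads differ?** The condition contrast averaged over evening and morning has trial-noise variance p(1−p)/30. At assumed accuracies of 60% and 90%, the SD ratio from trial noise alone is √(0.24/0.09) = 1.63. Adding the same between-child SD of 5, 10 or 15 percentage points to both groups lowers it to 1.38, 1.18 or 1.09. For the 10-point case: √[(80+100)/(30+100)] = 1.18. Unequal spread is plausible, but its size is unknown.

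**The case against.** The strongest reply is that this is a conditional weakness in a conventional analysis, not a demonstrated error. Several parts of that stand.

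- **Size of the error.** A reader might infer that the true error is 2% to 11%. The documents do not support that. Among the settings with at least 10 children per group, those figures need an assumed 2:1 size ratio together with a 2:1 SD ratio, and neither is reported. At an SD ratio of 1.25, for example, 20 v 15 gives 4.4% if ADHD is the more variable group.
- **Direction.** The TD losses do not by themselves point to false positives. Under equal recruitment with ADHD more variable, the PSG tests are conservative and the cost is power. If TD began as the larger group, losing five may even have narrowed the gap.
- **Other outcomes.** No imbalance is documented for actigraphy or No-Go. With equal groups of 10 to 30, the error is 5.2% to 5.5% even at an SD ratio of 2.
- **Scope.** It is tempting to say that every condition test is affected. The separate within-group No-Go ANOVAs use each group's own variance and stay at about 5%. A condition effect weighted by group size also stays at 5.0% to 5.5%; the result for the main effect depends on unweighted means.

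What remains is that the group × condition test pools the groups in all three sets of models. The within-group ANOVAs do not replace that test, and they are planned for inhibitory control only.

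**Conclusion.** The concern holds as a gap in the plan whose size cannot be fixed from the documents. The actigraphy, PSG and combined No-Go ANOVAs depend on equal contrast variances, or on equal group sizes, for the group × condition test and, with Type III means, for the condition main effect. Neither is secured, and PSG is the likeliest place for unequal sizes.

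For PSG from equal starts of 15 to 30 per group less five TD, the nominal 5% could be about 3% to 9% at an SD ratio of 2 in either direction. It would be about 3% to 4% if ADHD is the more variable group. At a ratio of 1.5, 15 v 10 gives 3.6% to 7.1%. With equal sizes it stays near 5%. These figures rest on assumed sizes, assumed SD ratios and normal contrasts. They do not show that any reported result is wrong. A change is worthwhile because it is cheap and removes the dependence, not because an inflated error has been shown.

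**What to change.** Keep the same effects, but do not pool the variance over groups:

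1. Compute each child's extension-minus-baseline contrast for every actigraphy and PSG outcome. For No-Go accuracy, average the contrast over evening and morning, and also compute the condition × time contrast.
2. Test group × condition, and group × condition × time for No-Go, with the Welch row of the SPSS independent-samples output (equal variances not assumed).
3. Estimate the overall condition effect as the unweighted mean of the two group means, with SE = 0.5 × √(s1²/n1 + s2²/n2) and Satterthwaite degrees of freedom. Treat the overall condition × time effect in the same way.
4. Report the group sizes and contrast SDs for each outcome, so that readers can see whether pooling would have mattered.

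The separate within-group No-Go ANOVAs need no change on this account. The work is one or two sentences in the SAP and a rerun on data already collected. If the spreads are in fact equal, the price is a few degrees of freedom and about 0.4 to 2 points of power in the cases checked.
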